## **Study Aims**

Aim 1. To assess the subjective and clinical effects of NR on ENDS users. Participants will undergo 2 ENDS use sessions that are preceded by 12-hour abstinence, with session order counter-balanced to mitigate order and carry-over effects. This study will focus on pre-post-use assessment of craving, withdrawal, satisfaction, intention to quit or use in the future, lung functions (e.g. FEV1 % predicted; FEV1/FVC, CO diffusing capacity-DLCO), and symptoms (e.g. dry mouth, eye irritation, palpitation, nausea). This aim will show ENDS users' response to NR on product satisfaction, dependence, lung functions and symptoms.

Aim 2. To assess puffing behavior in response to NR. Under the same protocol, puff topography (e.g. puff volume, puff frequency, duration) will be assessed continuously during the 2 sessions, while plasma nicotine will be measured pre-post sessions to assess nicotine boost and its correlation to puffing parameters. This aim will help understand users' compensatory puffing in response to NR and its effect on plasma nicotine.

Aim 3. To assess exposure to toxicants associated with NR. We will measure toxicant emissions (14 aldehydes) in the analytical lab using a smoking robot that reproduces the puff-by-puff behavior (playback) of each participant for all two nicotine conditions (Aims 1, 2). This aim will reveal how compensatory puffing behavior in response to NR influences acute exposure to pulmonary toxicants.

The proposed studies will give clear evidence on the potential of NR regulations to limit the addictiveness and use of ENDS, and to help predict any potential side effects of NR on ENDS users.

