## **Study Design**

This study is divided into 2 parts (studies), whereby the first part will be 2X2 comparing NJOY 5% and 3% to test the effects of partial nicotine reduction, and the second part will be using the NIDA Standardized Research Electronic Cigarette (SREC) for Clinical Research 5% and 0% (placebo), to test the effect of the total reduction using the same pods and juices from the same manufacturer.

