## **AIM 2: To assess the puffing behavior in response to nicotine reduction.**

**Objective and hypothesis.** This aim will help understand users' compensatory puffing behavior in response to NR and its effect on plasma nicotine as the main substance sustaining addiction to ENDS. *We hypothesize that NR-related compensatory puffing will be more pronounced in high vs. low-frequency users.*

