## Outcome measures

1. Aldehydes are determined using the method described in (Al Rashidi et al., 2008; El-Hellani et al., 2018). In brief, derivatized aldehyde-carbonyl species are extracted from the 2,4-dinitrophenylhydrazine cartridges in 90/10 (vol/vol) ethanol/acetonitrile and quantified by HPLC-UV. We will assess 14 priority aldehyde species that are associated with harm (Table 3).
2. Nicotine in the aerosol and ENDS liquid will be determined by GC-FID as described in (El-Hellani et al., 2015). In brief, nicotine in the aerosol is measured by immersing the filter pads collected in 6 mL water and shaking for 30 minutes. Then, 6 mL toluene is added to extract free-base nicotine. The last step is repeated twice to ensure complete extraction. A solution of NaOH (200 $\mu$ L) is then added to the mixture to convert protonated into free-base nicotine. Nicotine is then extracted using toluene. Total nicotine will be quantified by summing free-base and protonated nicotine.

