Demographic data will be examined and compared to determine if there are significant between-group differences on measures that may be related to study outcome (some differences are expected due to design such as past 30-day ENDS use) though these are expected to be minimized due to randomization. Unexpected between-group differences will be considered as potential adjustment covariates in the primary analysis (Evans et al., 2006). We will generate descriptive statistics which include means, standard deviations, frequencies, and proportions depending on the scale of the outcome by NR factor, time and group assignment. Univariate comparisons of the outcomes by the mentioned conditions will consist of repeated measures ANOVA and paired t-test (for 2X2 within factors) and two-sample t-test for between factor, or their non-parametric equivalents (Wilcoxon signed-rank test and Friedman test for within factors and Wilcoxon Mann-Whitney U test for between factor) if the parametric assumptions are not met. ANOVA will be followed by multiple comparisons with Bonferroni adjustments for multiplicity. Analysis of categorical outcomes will involve a chi-square test of independence for between factors or McNemar's test for paired proportions. The primary analysis of each outcome will involve analysis of variance with two within-subject factors (nicotine concentration: (5%, 3%) or (0% 5%)) and time (pre-post-use). This approach will be extended into a mixed-effects linear regression model to adjust or study the effects of personal attributes such as sex, education, race, and SES. Furthermore, we will consider clinical/physiologic factors such as lung function and respiratory symptoms in a similar modeling approach described above, as a function of experimental factors and demographic covariates, in order to quantify the harm or disease risk. In a case of a non-linear relationship between these factors, we will apply outcome transformations or use non-linear splines to accurately describe these outcomes as a function of

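### In the NJOY 5% v 3% part, the planned test of plasma nicotine has full compensation as its null, so a significant difference does not separate no compensation from partial compensation

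*Combined protocol and SAP*

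**What the plan says.** - **Role of plasma nicotine.** Under Study Aims, Aim 2, "plasma nicotine will be measured pre-post sessions to assess nicotine boost and its correlation to puffing parameters". The same aim is meant to clarify "compensatory puffing in response to NR and its effect on plasma nicotine".
- **Hypothesis by use frequency.** The Aim 2 section states: "We hypothesize that NR-related compensatory puffing will be more pronounced in high vs. low-frequency users".
- **Products.** Under Study Design, "the first part will be 2X2 comparing NJOY 5% and 3% to test the effects of partial nicotine reduction". The second part uses a research e-cigarette at 5% and 0%.
- **Model.** Under Statistical analysis: "The primary analysis of each outcome will involve analysis of variance with two within-subject factors", with concentration and time as the factors. Use frequency is not a term. Transformation is mentioned only for non-linear relationships. No ratio scale, compensation index or no-compensation reference is given for nicotine.
- **Playback nicotine.** Outcome measures (Aim 3), item 2: "Nicotine in the aerosol and ENDS liquid will be determined by GC-FID". The only analysis named specifically for the yield is a linear regression relating it to plasma nicotine.
- **Power.** The Sample size paragraph powers two within-subject factors, one between-subject factor (use frequency) and their interactions.

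**The concern.** For puff volume or puff number, no difference between concentrations means no compensation, so testing equality is natural. For nicotine actually taken in, the meaning is reversed. A person who puffs identically on a 3% and a 5% liquid takes in less nicotine from the 3% liquid. Only a person who makes up the whole shortfall shows equal boost. A significant ng/ml difference therefore shows that compensation was incomplete, but not whether there was any.

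This matters because topography alone does not show how far a change in puffing restored nicotine intake, and plasma nicotine and playback yield can. The effect of partial reduction on compensation and exposure is the second of the plan's three regulatory questions.

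The comparison by use frequency adds a scale problem. If frequent users usually take in more nicotine, their absolute drop is larger even when both groups compensate equally. Read at face value, this looks like less compensation in frequent users, the opposite of the Aim 2 hypothesis.

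**Working it through.** **1. The plan's own figures.** With 20% loss, 120/0.80 = 150, as stated. For repeated-measures ANOVA with m = 4 measurements and correlation 0.5, the noncentrality for within-subject effects and interactions is N x m x f²/(1 − 0.5). At N = 120 and f = 0.1 this is 120 x 4 x 0.01/0.5 = 9.6, giving power 0.867. At f = 0.2 power exceeds 0.99. For the between factor at f = 0.2 the noncentrality is 120 x 4 x 0.04/(1 + 3 x 0.5) = 7.68, giving power 0.785; at f = 0.1 power is 0.28. So the stated 80% is met for within-subject effects and interactions at N = 120. With 60 people in one part, within-subject power at f = 0.1 falls to 0.577. None of these figures concerns plasma nicotine specifically.

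**2. What the null means.** Let V be the 3%:5% ratio of total puff volume. If intake is proportional to concentration times volume, the boost ratio is R = (3/5) x V = 0.60V, and the fraction of full compensation is c = (R − 0.60)/(1 − 0.60).

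| c | R (boost) | V (volume) |
|---|---|---|
| 0 | 0.60 | 1.00 |
| 0.25 | 0.70 | 1.17 |
| 0.50 | 0.80 | 1.33 |
| 1 | 1.00 | 1.67 |

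The ANOVA null, R = 1, is the bottom row. The ratio must be taken on the boost (post minus pre). Post-session levels over a 2 ng/ml baseline with no compensation would give (2 + 0.6B)/(2 + B), which is 0.73 for a 5% boost B of 4 ng/ml and 0.65 for 15 ng/ml.

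**3. How often equality is rejected.** The documents give no plasma means or SDs, so these inputs are assumptions: 60 people in the NJOY part, lognormal boosts, log-SD 0.6 between people and 0.4 within person per session. Rejection is about 100%, 97%, 71% and 21% at c = 0, 0.25, 0.50 and 0.75. With other assumptions (CV 0.5–0.8, correlation 0.5–0.8) it is 98–100% at c = 0, 50–100% at c = 0.5 and about 5% at c = 1.

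**4. Testing against 0.60 instead.** The standard error of the mean log ratio is √2 x 0.4/√60 = 0.073. For R = 0.80, power = Φ(ln(0.80/0.60)/0.073 − 1.96) = 0.98, or about 0.82 if the within-person log-SD is 0.55. Under the other assumptions it is 88–100%, with about 5% rejection at c = 0.

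**5. Frequency contrast in ng/ml.** The drop is B x (1 − R). Take assumed 5% boosts of 5 (low-frequency) and 10 ng/ml (high-frequency).

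| Compensation, low / high | Drop, low | Drop, high |
|---|---|---|
| 0 / 0 | 5 x 0.4 = 2 | 10 x 0.4 = 4 |
| 0 / 0.5 | 5 x 0.4 = 2 | 10 x 0.2 = 2 |

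Equal compensation gives unequal drops, and unequal compensation gives equal drops. With 30 people per frequency group (an assumption) and the step 3 log-SDs, the ng/ml contrast is falsely significant in 5% of trials when usual boosts are equal, about 15% when they differ 1.5-fold and about 33% at 2-fold. Under the other assumptions, 5 v 10 ng/ml gives 27–89%. The log-ratio contrast stays near 5%. For the 0 / 0.5 row, the ng/ml contrast rejects about 5% of the time and the log ratio 34–96%.

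These simulations leave out LOQ substitution and non-positive boosts.

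**The case against.** A reader might infer that the planned ANOVA cannot measure compensation at all, or cannot compare it between frequency groups. The documents do not support that. They treat compensation as puffing behaviour and record puff volume, duration, number and inter-puff interval in both sessions. There equality is the right null. Half compensation implies a volume ratio of 1.33, and since ln(1.33) = ln(0.80/0.60), a test of that ratio against 1 has the same 98% power under the same log-SD. The Aim 2 frequency hypothesis is also worded about puffing, not plasma. Nowhere does the plan say that a plasma difference will be read as the degree of compensation. All of this stands, and it confines the point to plasma nicotine and playback yield.

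Three further objections stand in part.

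- The ANOVA means would allow a ratio to be calculated afterwards. That is true, but neither the ratio nor its reference is prespecified.
- Playback yield is a listed outcome, so the general model may cover it. It has no pre-session value, however, and a test of equal yield would again have full compensation as its null.
- The ng/ml frequency contrast is implied by the powered interactions but is not in the stated primary model. It misleads only if usual boosts differ between groups, which the documents do not show. With equal boosts it is valid.

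The value 0.60 is an inference from labelled strengths and proportional delivery. The plan does not state it.

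**Conclusion.** The point holds in a limited form. For 5% v 3% plasma nicotine, rejecting equal boost rules out full compensation but does not distinguish none from partial; under the assumed variability, rejection is likely anywhere from 0 to 50% compensation. Playback yield has no planned comparison with the liquid's own ratio. Topography still answers whether puffing changed. What is missing is a prespecified measure of how far that change restored nicotine intake.

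The meaning of the null follows from the 3/5 ratio and proportional delivery alone. The rejection rates also depend on assumed SDs, 60 people in the NJOY part and 30 per frequency group; the plan's 2X60 does not settle this split. The frequency distortion is conditional on unequal usual boosts. Separately, the primary model omits the frequency term that the Sample size paragraph powers, whatever scale is used. This is an inexpensive improvement to the analysis plan, not a flaw in the design.

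**What to change.** In the Statistical analysis section:

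1. Name the topography comparison as the main test of compensatory puffing. Topography has no pre-post levels, so this is a comparison by concentration only.
2. For the 5% v 3% part, prespecify the within-person 3%:5% ratio of playback nicotine yield (leading) and of plasma boost. Use a log-link model or a ratio of means for plasma.
3. Report each ratio with a 95% CI against the measured liquid concentration ratio (nominal 0.60); liquid nicotine is already to be assayed.
4. Add frequency and concentration x frequency to the model. Test the interaction on the ratio scale for these two outcomes.
5. State how boosts at or below zero, or affected by the 2 ng/ml LOQ substitution, are handled.
6. State that no such ratio exists for 5% v 0%, where compensation is judged from puffing.

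The cost is SAP wording and a little more analysis, with no new data. The downsides are reliance on proportional delivery, and plasma boosts that cannot be logged when non-positive or are distorted when LOQ-substituted. That is why playback yield should lead.

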Screening, and informed consent: Individuals who are identified as potentially eligible based on the phone screening will be asked to attend an onsite-screening, which will involve assessment of inclusion/exclusion criteria, physical examination, COVID-19 screening, and urine pregnancy testing for women. Prior to screening, potential participants will undergo a review of the study and consent procedures to ensure that they understand the study, its risks/benefits, and their rights as research participants. Consented (written) individuals will then undergo a physical examination conducted by the research nurse, who will have access to an on-call Medical Monitor (physician) in case of concern or for consultation at any point of the study as it is the standard practice in our lab. Successfully consented participants will be scheduled for their 1st session and asked to abstain from all tobacco/nicotine use 12 hours prior to it.

Sample size. All power calculations were performed with PASS19 (PASS, 2019). We built our calculation of the sample size for this study based on our preliminary study of the effect of NR on subjective (e.g. craving, urges) and puff topography measures (pls. see Preliminary Studies), where medium effect size (Cohen's  $f=0.2$ ) depending on nicotine condition was detected. Expecting a maximum 20% loss due to noncompliance with abstinence or study protocol (Vargas-Rivera et al., 2020), this study will include a dropout inflated sample of 150 ENDS users. Using repeated measures ANOVA F-test with 2 within and 1 between factors, a total dropout adjusted sample size of 120 (2X60) participants will have at least 80% power to detect small to medium-size effect (Cohen's  $f=0.1-0.2$ ) or larger for 2 within-subject (NR condition and time) and 1 between subject (use frequency) factors, as well as their interactions at 0.05 level of significance, assuming sphericity and a moderate correlation (0.5) among repeated measures (Cohen, 1988).

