## **AIM 1: To assess the subjective and clinical effects of nicotine reduction on ENDS users.**

Objective and hypothesis. This aim will help understand users' response to NR and how it will influence their product satisfaction, nicotine dependence, intention to quit or use in the future, lung functions, and clinical symptoms. We hypothesize that NR will be associated with less satisfaction, withdrawal suppression, and intention to use in the future and that such an effect will be more pronounced in total compared to partial NR and in high compared to low-frequency users.

Outcomes. We will utilize our clinical lab model to study the effect of NR on the following outcomes assessed according to the plan described in Table 2. All assessments will be based on instruments that are standard in clinical lab studies of addictive behaviors modified for the ENDS we plan to use (Vargas-Rivera et al., 2020). Participants will use a tablet to respond to these measures using RedCap.

**Outcomes.** We will utilize our clinical lab model to study the effect of NR on the following outcomes assessed according to the plan described in Table 2. All assessments will be based on instruments that are standard in clinical lab studies of addictive behaviors modified for the ENDS we plan to use (Vargas-Rivera et al., 2020). Participants will use a tablet to respond to these measures using RedCap. Briefly, we will assess;

1. Demographic and baseline characteristics; including age, race, sex, and reasons for ENDS use. Other characteristics will include the frequency of ENDS use, and the history of other tobacco/nicotine products use (Amato, Boyle & Levy, 2016; Zavala-Arciniega et al., 2019; Vargas-Rivera et al., 2020).
2. Dependence measures including; 1) *Use satisfaction* (Modified Cigarette Evaluation Questionnaire (mCEQ) (Arger et al., 2017); 2) *Dependence* (Questionnaire of Smoking Urges-brief and the Minnesota Nicotine Withdrawal Scale, Penn State Electronic Cigarette Dependence Index (Ben Taleb et al., 2018; Foulds et al., 2015; St Helen et al., 2017); 3) *Puff sensory effects* (Duke Sensory Scale, (Malson & Pickworth, 2002)).

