mentioned covariates. Given the known sex-related differences in nicotine dependence (Benowitz et al., 2006), to assess if sex has any effect on the results, it will be considered as a covariate and we will test the pre-planned interaction with it to determine the heterogeneity of the study outcomes by sex as well as potential differential effects. Similarly, for categorical outcomes we will apply generalized linear models and estimating equations with the same main effects as described above, modeling within factors as random effects. We will test for the carry-over effect statistically and will control for it when testing for the primary factors (Senn, 2002).

For Aim 3, we will use a one-way ANOVA to test the effect of NR on aldehyde emissions and multiple linear regression analysis to assess the influence of puff topography data (puff volume, duration, number, and interpuff interval) on aldehyde emissions. Additionally, we will measure the relation between the plasma nicotine levels obtained in the clinical lab and measured nicotine yields obtained in the analytical lab using linear regression. Significance levels will be adjusted for violations of the sphericity assumption using Huynh-Feldt corrections (Keppel, 1991). All differences will be considered significant at the alpha level of 0.05 using adjusted p-values where appropriate. Due to the nature of laboratory data collection, missing data is rare and it usually occurs due to instrument malfunction. All data are collected and checked for completeness by laboratory staff. In the case of missing data, which we expect to be minimal, we will use a regression model based on multiple imputations with all available outcome data, demographic, and clinical variables as predictors. This will be carried out in 25 random repetitions under missing at random assumption, analyzed using methods described above and results will be combined to produce unbiased overall estimates and standard errors of the experimental conditions. As a sensitivity analysis completers results will be compared with multiple imputation results.

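### The primary nicotine-by-time ANOVA names no test term, and a post-use comparison adjusted for the pre-use value would be at least as precise as either candidate

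*Combined protocol and SAP*

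**What the plan says.** The Statistical analysis section gives one primary method for every outcome: an ANOVA with "two within-subject factors (nicotine concentration: (5%, 3%) or (0% 5%)) and time (pre-post-use"). No term of that model is named as the test. Its mixed-model extension lists personal attributes as covariates; the session's pre-use value is not among them. Follow-up testing is described only in general terms: "ANOVA will be followed by multiple comparisons with Bonferroni adjustments for multiplicity".

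Two other places bear on the choice of term:

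- The AIM 1 hypothesis is that "NR will be associated with less satisfaction, withdrawal suppression, and intention to use in the future". Suppression of withdrawal is a pre-to-post change, which points to the interaction, but the plan does not say so.
- The sample size paragraph (Participants and recruitment) claims at least 80% power at f = 0.1 to 0.2 for both within-person factors and use frequency, "as well as their interactions at 0.05 level of significance". It assumes "a moderate correlation (0.5) among repeated measures" and rests on "a total dropout adjusted sample size of 120 (2X60) participants".

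Table 2 schedules urges, withdrawal, harm perception, intention and plasma nicotine both before and after use. The AIM 1 outcome list does the same for lung function and some symptoms.

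**The concern.** There are two linked problems.

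1. With two candidate terms and none named, the primary p-value can be chosen once results are known.
2. Neither term is a good default. The pre-use value precedes that session's exposure, so without carry-over nicotine can shift only the post-use value. The main effect averages pre and post, and so estimates half of a post-use difference. The interaction subtracts a noisy pre-use difference at full weight. Which one performs worse depends on correlations that the documents do not give by outcome.

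At stake is the power to detect small effects in each part of the study, using data that are already being collected.

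**Working it through.** **Reproducing the plan's figure.** Inputs from the sample size paragraph: N = 120, four repeated measures (2 conditions × 2 times), correlation 0.5, alpha 0.05.

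- Within-person terms at f = 0.1: noncentrality = 120 × 4 × 0.1² / (1 − 0.5) = 9.6, power 0.867.
- Between-person factor at f = 0.2: 120 × 4 × 0.2² / (1 + 3 × 0.5) = 7.68, power 0.785.
- Inflation: 120 / 0.8 = 150.

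The claim is thus reproduced to within 2 points if all 120 people enter one analysis.

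**People per contrast.** AIM 3 counts 240 topography sessions. At two per person that is 120 people over both parts, or 60 per nicotine contrast if split equally (assumed; 2X60 could instead mean the two use-frequency groups). Then 60 × 4 × 0.1² / 0.5 = 4.8, power 0.577.

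**Comparing the tests.** Set the SD to 1 and let the four cell means be 0, 0, 0, d. Both ANOVA terms then have f = d/4, so f = 0.10, 0.15, 0.20 means d = 0.4, 0.6, 0.8 SD. Let D_post and D_pre be the between-session differences after and before use:

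- var(D_post) = var(D_pre) = 2(1 − r_between)
- cov = 2(r_same − r_cross), where r_same links pre and post within a session and r_cross links them across sessions

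Variances of the estimated post-use effect:

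- Interaction: var(D_post) + var(D_pre) − 2cov
- Main effect, rescaled to the full effect: var(D_post) + var(D_pre) + 2cov
- Adjusted post-use: var(D_post) − cov²/var(D_pre)
- Unadjusted post-use: var(D_post)

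The interaction is D_post − D_pre and the rescaled main effect is D_post + D_pre. They fix the pre-use coefficient at 1 and −1; adjustment estimates the best value. Hence neither can beat it, apart from the degree of freedom spent. This also holds when pre- and post-use variances differ.

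Power comes from the noncentral F with n − 2 df (n − 3 if adjusted) and noncentrality n·d²/variance. For n = 60, d = 0.4, other correlations 0.5, in the order interaction / main / adjusted / unadjusted:

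| Same-session correlation | Variances | Power |
|---|---|---|
| 0.5 | 2.0 / 2.0 / 1.0 / 1.0 | 0.58 / 0.58 / 0.86 / 0.86 |
| 0.7 | 1.2 / 2.8 / 0.84 / 1.0 | 0.79 / 0.44 / 0.91 / 0.86 |
| 0.8 | 0.8 / 3.2 / 0.64 / 1.0 | 0.93 / 0.40 / 0.97 / 0.86 |
| 0.9 | 0.4 / 3.6 / 0.36 / 1.0 | 0.998 / 0.36 / 0.999 / 0.86 |

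At equal correlations of 0.5, 80% power for d = 0.4 needs 101 people with either ANOVA term and 52 with the adjusted model (53 allowing for estimation of the slope).

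**Range.**

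- All correlations 0.3 or 0.7 (n = 60, d = 0.4): 0.44 versus 0.73, or 0.79 versus 0.98.
- N = 120, all correlations 0.5, d = 0.4: 0.87 versus 0.99.
- f = 0.15, n = 60, all correlations 0.5: 0.90 versus 0.995.
- f = 0.2, n = 60: the interaction is at least 0.99 throughout; the main effect is 0.99, 0.95, 0.93, 0.89 at same-session correlation 0.5, 0.7, 0.8, 0.9.
- Pre-use SD 0.25 or 0.5 of the post-use SD (assumed, as may hold for plasma nicotine after abstinence), correlations 0.5: interaction 0.84 or 0.78 versus 0.86.
- The interaction overtakes the unadjusted post-use comparison when r_same − r_cross exceeds (1 − r_between)/2: a same-session correlation of 0.65, 0.75 or 0.85 if the others are 0.3, 0.5 or 0.7.

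**Simulation.** A two-period crossover with a fitted 0.2 SD period effect (6,000 trials, n = 60, d = 0.4, correlations 0.5) gave 0.579, 0.575, 0.859 and 0.866 in the table's order. Under the null, rejection was 0.044 to 0.053 for all four tests (4,000 trials).

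**The case against.** The strongest reply is that only the unnamed term is a defect and the rest is a preference. Both terms are valid without carry-over, and the hypotheses speak of change, so a reader would take the interaction. In the headline case of equal correlations, the covariate adds nothing over an unadjusted post-use contrast (0.86 each). The covariate helps only when same-session correlation exceeds cross-session correlation, and there the interaction catches up. The shortfall below 80% also needs the smallest effect and n = 60. At f = 0.2, the effect that "depending on nicotine condition was detected" in the preliminary study, the interaction is ample.

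Much of this stands and limits the size of the point. At equal correlations the gain comes solely from not averaging in or subtracting the pre-use value. Naming the term would also leave open the choice among outcomes.

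It does not remove the point. The interaction is inferred, never stated, while the sample size paragraph covers every term. An unadjusted post-use contrast could fall under the listed paired t-tests or the Bonferroni follow-up, but neither names it and neither is primary. Within a Bonferroni set of two or four comparisons (counts assumed) its power would be 0.79 or 0.70 at f = 0.1, n = 60, correlations 0.5. Because the correlations are unknown, the adjusted model is the safe choice: the interaction does poorly when same-session correlation is low, and the main effect when it is high.

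**Conclusion.** The point holds. The primary test is not identified, and for pre/post outcomes the adjusted post-use comparison is never materially less efficient than either ANOVA term. Under the plan's correlation of 0.5 the variance ratio is 2, which at f = 0.1 and 60 per contrast means power of 0.58 versus 0.86.

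This assumes no carry-over into the second session's pre-use value, equal correlations and SDs in the headline case, and an equal split between parts. The power gain is mainly for effects below f = 0.2. It does not extend to outcomes with no pre-use value. It is a worthwhile, inexpensive improvement; the planned ANOVA is not invalid.

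**What to change.** For each part, and for outcomes measured before and after use:

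- Make the primary model a mixed model of the post-use value on nicotine, period, sequence and use frequency, with participant as a random effect.
- Add two covariates: the participant's mean pre-use value and the session's deviation from it. A single slope on the raw pre-use value blends within- and between-person relations and, at equal correlations of 0.5, lowers the variance advantage from 2.0 to 1.67.
- Name the nicotine coefficient as the test and keep nicotine-by-time as secondary.
- Because the second session's pre-use value follows the first session's exposure, keep the planned carry-over check and report the model without baseline terms as a sensitivity analysis.

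Two clarifications belong with this. Satisfaction, the visual analogue scale, the sensory scale and topography have no pre-use value in Table 2, so state the same model without baseline terms for them. Aldehydes already have their own statement: "we will use a one-way ANOVA to test the effect of NR on aldehyde emissions". Also reconcile Study Aims, which lists satisfaction among the pre-post measures, with Table 2, which shows it after use only.

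The cost is SAP wording, two covariate terms per model (one degree of freedom from the within-person test) and one sensitivity analysis. No new data, visits or participants are needed.
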